## **B. Medical History**

Medical histories will be coded using the MedDRA version 24.1 and summarized by System Organ Class (SOC) and Preferred Term (PT) by dose cohort for each module separately.

A data listing will also be provided.

## **C. Disposition**

Disposition will be summarized as the number and percentage of patients enrolled, dosed, discontinued from study treatment along with the reason for discontinuation and discontinued from the study along with the reasons for discontinuation by dose cohort and overall, for each module separately. The number of subjects in each analysis population will be summarized separately.

Enrollment and disposition will be listed in a data listing. Screen failures will also be listed.

## **D. Protocol Deviations**

A summary of number and percentage of patients with any protocol deviation by dose cohort and module based on the Safety Population will be present.

Protocol deviation would be classified into major and minor. protocol deviation will be summarized by major/minor category. In addition, COVID-19 related protocol deviations will be summarized.

# **VIII. Efficacy Analyses**

Efficacy analyses will be based on the Efficacy Evaluation Population.

## **A. Efficacy Endpoints**

The preliminary assessment of efficacy will be assessed via tumor responses and lesion parameters based on the RECIST version 1.1. guidelines. The efficacy analyses of responses including best overall response (BOR), objective response rate (ORR),

duration of response (DoR), disease control rate (DCR) and progression free survival (PFS). The lesion parameters include change and percent change from baseline in the sum of the diameters of target lesions (TLs), presence/absence of non-target lesions and/or new lesions.

All efficacy endpoints will be summarized and analyzed by dose cohorts for Module 1, Module 2 and Module 3 separately unless otherwise specified below.

### 1. Best Overall Response (BOR)

Categorization of objective tumor response based on RECIST 1.1. guidelines for target lesions include CR (complete response), PR (partial response), SD (stable disease), PD (progression of disease), and NE (not evaluable).

Best overall response is determined based on the RECIST overall responses as assessed by the investigator from the start of first study treatment (RXC004 or Nivolumab if relevant, whichever is earlier) until the end of last study treatment, including any required RECIST scans/assessments for confirmation post the last study treatment.

CR and PR can only be considered as the best overall response if the initial CR or PR is confirmed by a scan that shows the same response or better at least 4 weeks after the initial response. If the repeat scan following the initial response is NE, but the next evaluable response confirms the initial CR/PR response, the BOR of CR/PR will be claimed. For example, a patient with time point responses assessed as PR-NE-PR will be considered as a confirmed PR.

SD does not require confirmation. If SD is the best response ever seen and it meets the minimum criteria for SD duration (at least 35 days from date of first study treatment), SD will be claimed to be the best response overall response.

Below table illustrates the determination of the best overall response when CR or PR confirmation is required.

**Table 3. Best Overall Response When Confirmation of CR and PR Required**

Overall response Initial response	Overall response Subsequent response	Best overall response
CR	CR	CR
CR	PR	PR
CR	SD	SD provided minimum criteria for SD duration met, otherwise PD
CR	PD	SD provided minimum criteria for SD duration met, otherwise PD

CR	NE	SD provided minimum criteria for SD duration met, otherwise NE
PR	CR	PR
PR	PR	PR
PR	SD	SD provided minimum criteria for SD duration met, otherwise PD
PR	PD	SD provided minimum criteria for SD duration met, otherwise PD
PR	NE	SD provided minimum criteria for SD duration met, otherwise NE
SD	SD	SD provided minimum criteria for SD duration met, otherwise NE
SD	PD	SD provided minimum criteria for SD duration met, otherwise PD
SD	NE/Missing	SD provided minimum criteria for SD duration met, otherwise NE
PD	Not applicable	PD
NE	NE	NE

## 2. Objective Response Rate (ORR)

Objective response rate is defined as proportion of patients with a BOR of CR or PR prior to any evidence of progression (as defined by RECIST 1.1).

## 3. Disease Control Rate (DCR)

Disease control rate is defined as the proportion of all patients dosed that have a visit response of at least SD, PR, or CR at the second schedule scan post baseline, scheduled at week 12 for module 1 and module 3 or week 16 for module 2. Therefore, earlier visit responses of CR, PR that become PD at the second post baseline scan or NE responses at the second post baseline scan do not constitute disease control. A time window of 1 week around the visit will be applied and any visits occurring within 1 week of the scheduled time will be acceptable for inclusion in the assessment; however, if an earlier visit is defined as PD, then the visit response at the second post baseline scan would also be defined as PD. If the second post baseline scan is missing or NE, but the next evaluable response is SD or better, then the patient will be defined as having non-progressive disease at the second post baseline scan visit. Disease control rate will also be assessed separately for the first 3 scheduled post baseline scans (i.e., 18 weeks for module 1 and 3 and 24 weeks for module 2. A separate line in the ORR table will be presented to show the DCR for the

first 2 scan visits and DCR for the first 3 scan visits.

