## Analysis Populations

Four analysis populations will be defined for use with various analyses.

- The Safety Population will consist of all patients who enrolled and receive at least one dose of study drug.
- The PK Evaluable Population will consist of those patients deemed by the sponsor or pharmacokineticist to have sufficient PK concentration data to be meaningfully included in the PK analysis summaries.
- The PD Evaluable Population will consist of those patients deemed by the sponsor or translational scientist to have sufficient PD assessment data to be meaningfully included in the PD analysis summaries.
- The Efficacy Evaluable Population will include patients who receive a radiographic assessment at baseline, received at least one dose of study treatment, and at least one post-dose radiographic tumour assessment, or progressed ahead of the first scan.

Adverse events and medical history will be coded using the Medical Dictionary for Regulatory Activities (MedDRA) version 20.0 or greater. Concomitant medications will be coded using the World Health Organization Drug Dictionary (WHODrug: March 2017 or later version).

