### 9.2.1 Efficacy Analyses

Overall Response Rate (ORR) (CR+PR), Duration of Response (DoR), Disease Control Rate (DCR) (CR+PR+SD) will be calculated for the efficacy evaluable population based on modified RECIST guidelines (Appendix 4).

At each tumour assessment visit patients will be programmatically assigned a RECIST 1.1 visit response of CR, PR, SD, PD or NE depending on the status of their disease compared with baseline and previous visit assessments.

Progression of target lesions (TLs) will be calculated in comparison to when the tumour burden was at a minimum (i.e., smallest sum of diameters previously recorded on study, including baseline). In the absence of progression, tumour response (CR, PR, SD) will be calculated in comparison to the baseline tumour measurements obtained before starting treatment.

The best overall response will be determined programmatically for each patient as CR, PR, SD, PD or NE, based on the best response recorded from start of study treatment to end of treatment, including any assessments for confirmation after the end of treatment.

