### Objective Response Rate

Objective response rate is defined as the number of patients who have at least one response of CR or PR prior to any evidence of progression (as defined by RECIST 1.1) that is confirmed at least 4 weeks later divided by the number of response evaluable patients.

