### **Disease Control rate**

Disease control rate is defined as the proportion of all patients dosed that have a visit response of at least SD, PR or CR at the second schedule scan post baseline, scheduled at week 12 for module 1 or week 16 for module 2. Therefore, earlier visit responses of CR, PR that become PD at the second post baseline scan or NE responses at the second post baseline scan do not constitute disease control. A time window of 1 week around the visit will be applied and it is recommended that any visits occurring within 1 week of the scheduled time will be acceptable; however, if an earlier visit is defined as PD then the visit response at the second post baseline scan would also be defined as PD. If the second post baseline scan is missing or NE, but the next evaluable response is SD or better, then the patient will be defined as having non-progressive disease at the second post baseline scan visit. Disease control rate will also be assessed for patients who have at least SD for the first 3 scheduled post baseline scans (ie 18 weeks for module 1 and 24 weeks for module 2).

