### **2. Efficacy Evaluable Population**

The Efficacy Evaluable Population will include patients who receive a radiographic assessment at baseline, received at least one dose of any study treatment, and at least one post-dose radiographic tumor assessment, or progressed or died ahead of the first scan. The efficacy evaluable population will be used for the efficacy analyses.

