## **B. Efficacy Endpoint Analyses**

ORR and DCR will be summarized for all dose levels. The two-sided 95% confidence interval (CI) using the Clopper-Pearson method will only be provided at RP2D and overall.

PFS, and DoR will be summarized using the Kaplan-Meier (KM) method at by treatment group and overall. Estimates of median and PFS at 6 and 12 months, with the corresponding 95% CI will be reported for RP2D and overall. Swim lane plot for all time to event analysis by dose level and by wnt ligand dependency (DOR, PFS and duration of treatment).

Time to response, defined as (date of first documented response of CR or PR for patients who have a confirmed CR or PR – date of first treatment + 1) / 7, will be summarized descriptively among patients who reported a response.

Percent change from baseline in the sum of diameters of TLs will be summarized descriptively. Percent change from baseline in the sum of diameters of TLs for individual patient will be present in the spider plots – separate plots will be done by dose level and by Wnt ligand dependency. The best percent change in tumor size while on treatment will be presented in two waterfall plots. In one plot the bars will be color coded by dose level and in a separate plot by Wnt ligand dependency.

ORR and percent change in the sum of TL diameters will only be evaluated among patients with measurable disease (i.e., with target lesion identified) at baseline. All efficacy data as collected on the eCRF along with the derived parameters will be presented in data listings.

Given the small sample size in module 3, Duration of Response (DoR) and Time to Response will not be summarized for module 3 patients.

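### DCR is defined on all dosed patients but assigned to the Efficacy Evaluable Population, so its denominator is not fixed

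*SAP*

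**What the plan says.** **Endpoint definitions.** SAP VIII.A.3: "Disease control rate is defined as the proportion of all patients dosed that have a visit response of at least SD, PR, or CR", judged at the second scheduled scan after baseline (week 12 in Modules 1 and 3, week 16 in Module 2). The protocol's Disease Control rate paragraph in 9.2.1 begins the same way: "Disease control rate is defined as the proportion of all patients dosed".

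**Population assignments.** The opening of protocol 9.2.1 says: "Disease Control Rate (DCR) (CR+PR+SD) will be calculated for the efficacy evaluable population". SAP VI.J.2 says: "The efficacy evaluable population will be used for the efficacy analyses". SAP VIII opens with: "Efficacy analyses will be based on the Efficacy Evaluation Population", and VIII.A lists DCR among those analyses.

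**The neighbouring endpoint.** The protocol's ORR definition, placed directly before the DCR definition, is "divided by the number of response evaluable patients".

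**The EE Population.** Both documents require a baseline scan and at least one dose. The protocol adds: "at least one post-dose radiographic tumour assessment, or progressed ahead of the first scan". SAP VI.J.2 also admits patients who died before the first scan.

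**Reporting.** SAP VIII.B summarises DCR at every dose level, with a two-sided 95% interval "using the Clopper-Pearson method will only be provided at RP2D and overall". It gives no N for DCR.

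**The concern.** The plan gives two denominators for one rate and no rule for choosing between them. The set of all dosed patients is the Safety Population, which the SAP assigns to safety analyses only, so a programmer following the section header and one following the endpoint definition would produce different tables.

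The choice is not neutral. Disease control needs a visit response of stable disease or better. A dosed patient without a baseline scan, or without any post-dose scan, has no such response. Removing that patient shrinks the denominator and leaves the numerator alone.

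DCR also carries weight in this trial. Protocol 1.2.1 argues that the drug may produce prolonged stable disease rather than shrinkage, and even calls DCR the primary endpoint for monotherapy, although the formal objectives (1.9) make anti-tumour activity secondary. If the denominator is settled only after the data are seen, one of the two options can only favour the drug.

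**Working it through.** The documents contain no power, alpha or target rate that depends on this denominator, so there is no planned figure to reproduce. The check has two parts.

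**1. Does the text resolve the conflict?**

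| Place | Denominator for DCR |
|---|---|
| Protocol 9.2.1, opening paragraph | EE Population |
| Protocol 9.2.1, Disease Control rate | All dosed |
| SAP VI.J.2 and opening of VIII | EE Population (all efficacy analyses) |
| SAP VIII.A.3 | All dosed |
| SAP VIII.B | Not stated |

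No exception for DCR and no order of precedence appears in either document. SAP VIII.A.3 places DCR as a line in the ORR table, and SAP VIII.B limits ORR to patients with measurable disease, so a reader of that table could also assume a third denominator.

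**2. How far can the rate move?**

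Let x be the number controlled, D the number dosed, and m the number dosed but outside EE. None of the m can be among the x.

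- All-dosed rate: x/D
- EE rate: x/(D−m)
- Ratio: [x/(D−m)] / [x/D] = D/(D−m), whatever x is (x > 0)

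Inputs for D: the 2 mg cohort had 6 patients (protocol 5.4.3); Module 2 plans approximately 18 (protocol 9.1); Module 1 dosed 4+3+7+6+4+1 = 25 (protocol 5.4.3). Module 3 counts six *evaluable* patients per arm, so the number dosed may be higher; 7 and 8 are assumed.

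| D | m = 0 | m = 1 | m = 2 |
|---|---|---|---|
| 6 | 1.00 | 6/5 = 1.20 | 6/4 = 1.50 |
| 7 | 1.00 | 7/6 = 1.17 | – |
| 8 | 1.00 | 8/7 = 1.14 | – |
| 18 | 1.00 | 18/17 = 1.06 | 18/16 = 1.13 |
| 25 | 1.00 | 25/24 = 1.04 | 25/23 = 1.09 |

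The values of m are assumptions. For D = 6 and m = 1, with an assumed 1, 2 or 3 patients controlled and exact Clopper-Pearson 95% intervals:

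| Controlled | All dosed | EE |
|---|---|---|
| 1 | 1/6 = 16.7% (0.4–64.1) | 1/5 = 20.0% (0.5–71.6) |
| 2 | 2/6 = 33.3% (4.3–77.7) | 2/5 = 40.0% (5.3–85.3) |
| 3 | 3/6 = 50.0% (11.8–88.2) | 3/5 = 60.0% (14.7–94.7) |

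Protocol 1.7.1.1 reports stable disease in 5 of 18 RECIST-evaluable Module 1 patients. Purely as an illustration, 5/18 = 27.8% (9.7–53.5) and 5/25 = 20.0% (6.8–40.7). These are not the trial's DCR: the five are not stated to be week-12 disease control, the 18 need not equal the EE count, and the two counts may come from different data cuts.

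**The case against.** The best case for leaving the text alone has four parts.

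- **A reconciling reading.** SAP VIII sets the population for everything beneath it, so the definition could mean all patients within EE, as opposed to only those with target lesions. Neither document says this. EE membership already requires a dose, so on this reading the word *dosed* would add nothing.
- **Loose drafting.** The sentence opening protocol 9.2.1 names ORR, DoR and DCR together and assigns all three to EE, which counts against a deliberate difference between ORR and DCR. This is fair: intent cannot be proved. But adjacent definitions that use different denominators show that the wording cannot simply be read past.
- **Few patients are affected.** Eligibility requires a baseline assessment within 28 days of the first dose, SAP EE keeps patients who progressed or died before the first scan, and protocol 7.1 continues follow-up after stopping treatment unless consent is withdrawn. This stands. The group is mainly early withdrawals and losses, and it may be empty. It is not hypothetical to the SAP, however: the PFS rules in VIII.A.5 provide for patients with no evaluable visits or no baseline data.
- **Low stakes.** Efficacy is descriptive, the intervals at six patients overlap almost entirely, and population counts (SAP VII.C) and efficacy listings (SAP VIII.B) would let a reader recompute either rate. This limits the harm. It does not fix the choice in advance.

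**Conclusion.** The concern holds. Both documents state two incompatible denominators for DCR, and nothing in them settles which applies. The EE choice multiplies the all-dosed rate by D/(D−m). It therefore has no effect if every dosed patient is in EE, a factor of 1.20 for one excluded patient in the six-patient 2 mg cohort, and 1.04 for one in all of Module 1. The direction follows from the definitions; the size depends on m, which the documents do not give. No hypothesis test or error rate is involved. What is affected is the reported DCR and its interval at the RP2D and overall. The point should be corrected, but it does not threaten the study's primary safety objective.

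**What to change.** - State in SAP VIII and VIII.A.3 that DCR uses all dosed patients (the Safety Population), as the definition in both documents already says, and that dosed patients without a qualifying response count as not controlled. Keep the existing rule for a missing or non-evaluable second scan followed by stable disease or better.
- Print DCR with its own N in the ORR table, and give the EE version, using the SAP's EE definition, as a supportive line.
- Reconcile the opening of protocol 9.2.1 with its DCR definition, or record in the SAP the departure from the former.
- Apply this to modules whose databases are not yet locked. The Module 1 database is already locked (SAP I), so state in its study report which denominator was used.

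Rewriting the definition to EE would also remove the contradiction. The all-dosed version is preferable because it keeps the written endpoint definition and cannot be raised by early losses.

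The cost is a few sentences in the SAP, one extra table line and a note or amendment for the protocol. The headline DCR may be slightly lower.

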## 1.9.2 Secondary Objectives

The following secondary objectives apply to all modules of the study:

- To characterise the PK profile of RXC004, following a single dose and at steady state after multiple dosing, when given orally alone or in combination with anti-cancer treatments.
- To obtain a preliminary assessment of RXC004 activity by evaluation of pharmacodynamic biomarker changes which may include, but are not limited to, Wnt pathway inhibition, gene expression signatures, and ctDNA levels.
- To obtain a preliminary assessment of the anti-tumour activity of RXC004 as a single agent or in combination with anti-cancer treatments (to include assessment of ORR, DCR, DoR and PFS).

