### **2.3.1.3 Subsequent Therapies for Cancer**

Details of first and subsequent therapies for cancer and/or details of surgery for the treatment of the cancer, after discontinuation of treatment, will be collected. Reasons for starting subsequent anti-cancer therapies including access to other PORCN/Wnt pathway inhibitors or investigational drugs will be collected and included in the exploratory assessments.

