#### Tumour Assessments

RECIST 1.1 guidelines for measurable, non-measurable, target lesions (TLs) and non-target lesions (NTLs) and the objective tumour response criteria are presented in Appendix 4 of this Clinical Study Protocol.

Baseline scans for RECIST should be performed within 28 days of first dose (the use of scans obtained as part of standard clinical practice, prior to informed consent, but within the 28-day period should be detailed in the consent form). Baseline tumour assessments should encompass all areas of known predilection for metastases in the disease under evaluation and should additionally investigate areas that may be involved based on signs and symptoms of individual patients. Baseline assessments should be performed no more than 28 days before the start of study treatment, and ideally should be performed as close as possible to the start of study treatment.

Tumour assessments will be performed using full body (chest, abdomen and pelvis) CT/ MRI for soft-tissue lesion only and bone scan (with additional confirmatory imaging – plain x-ray, CT/ MRI) for bone metastasis (in patients who develop bone metastasis after study start). The methods of assessment used at baseline should be used at each subsequent follow-up assessment.

Scans will take place at timepoints detailed in the Schedule of assessments (Appendix 1, Appendix 20 and Appendix 9). Scans may be performed at other times, as clinically indicated.

Imaging tumour assessments will cease at objective progression. In the event of a patient discontinuing treatment for reasons other than progression they should continue to be followed for progression unless there is withdrawal of consent. Progression criteria for imaging tumour assessment will be determined by the following assessments:

- RECIST criteria for soft-tissue lesions only (lymph nodes, visceral metastasis, prostate)
- Bone Scans will be conducted at screening/baseline to rule out bone metastasis and during treatment if investigator suspects disease progression/development of bone metastasis

Any other sites at which new disease is suspected should also be appropriately imaged. If an unscheduled assessment is performed and the patient has not progressed, every attempt should

be made to perform subsequent assessments at the scheduled visits whilst the patient remains on study treatment.

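### Disease control can be scored from a scan taken after another anti-cancer therapy has started, because the DCR rule, unlike those for BOR and PFS, does not deal with that event

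*SAP*

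**What the plan says.** SAP VIII.A.3 defines the endpoint: "Disease control rate is defined as the proportion of all patients dosed that have a visit response of at least SD, PR, or CR". The response is read from scheduled scan number two after baseline, which falls at week 12 in Modules 1 and 3 and week 16 in Module 2. A second DCR covers the first three scans (week 18, or week 24 in Module 2). Protocol 9.2.1 gives the same definition for Modules 1 and 2.

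Two further rules in SAP VIII.A.3 matter here:
- An earlier progression is carried forward: "if an earlier visit is defined as PD, then the visit response at the second post baseline scan would also be defined as PD".
- A gap can be filled by a later scan: "If the second post baseline scan is missing or NE, but the next evaluable response is SD or better", the patient is treated as non-progressive at the second scan.

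Protocol 7.1 (Tumour Assessments) says of patients who stop treatment for reasons other than progression that "they should continue to be followed for progression unless there is withdrawal of consent". Protocol 2.3.1.3 adds: "Details of first and subsequent therapies for cancer and/or details of surgery for the treatment of the cancer, after discontinuation of treatment, will be collected". SAP IX.J summarises and lists that therapy but does not link it to any response endpoint.

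The stated secondary objective (protocol 1.9.2) is a "preliminary assessment of the anti-tumour activity of RXC004 as a single agent or in combination with anti-cancer treatments".

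**The concern.** The objective concerns what RXC004 does, alone or with its study partner. A patient who leaves study treatment early without RECIST progression, starts a different drug and is stable at week 12 satisfies the DCR rule as written. The stability then observed may belong to the second drug. The error can only raise DCR, because the early stop is turned into a success.

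The expected form of benefit makes this more relevant. Protocol 1.2.1 anticipates prolonged stable disease rather than shrinkage, and SD is the category that disease control mainly counts. With arms of about six patients, one such case is visible in the result.

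**Working it through.** The plan states no target DCR, alpha or power, so there is no design figure to reproduce. The check compares the endpoint rules and then sizes the effect per patient.

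**1. Which patients are exposed.** Four conditions must all hold: study treatment stopped; no RECIST PD at or before the relevant scan (otherwise the carry-forward rule applies); another anti-cancer therapy started before that scan; and the scan shows SD or better.

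**2. Whether such scans can exist.** They can.
- Protocol 3.6 and 7.1 continue follow-up to progression after a stop for another reason.
- Tables 2, 4 and 7 of the protocol list permanent discontinuations that are not progression, such as fragility fracture, BMD loss and recurrent toxicity. Protocol 3.6 adds patient decision.
- The schedules of assessments record subsequent anti-cancer therapy in the same follow-up period in which scans continue.
- Protocol 2.3.1.1 restricts other anti-cancer agents during the study, but 2.3.1.3 expressly expects them after discontinuation.
- Protocol 5.4 gives a median RXC004 exposure in Module 1 of about 7 weeks. The DCR scan is at week 12, which is 12 − 7 = 5 weeks later. The documents do not say how many of those who had stopped did so without progression.

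**3. How far the fill-in rule extends the window.** If the second scan is missing or NE, the next scheduled scan is 18 − 12 = 6 weeks later in Modules 1 and 3, and 24 − 16 = 8 weeks later in Module 2.

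**4. How each endpoint treats the event.**

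| Endpoint | Rule on scans after study treatment or new therapy |
|---|---|
| BOR, and through it ORR (SAP VIII.A.1–2) | Assessments to end of last study treatment, "including any required RECIST scans/assessments for confirmation post the last study treatment" |
| Best change in tumour size (SAP VIII.A.5, VIII.B) | On treatment only |
| PFS (SAP VIII.A.5) | New therapy expressly ignored |
| DCR (SAP VIII.A.3) | Nothing stated |

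A patient who stops at week 4 with no on-treatment scan, and is SD at week 12 on another drug, could therefore have no evaluable BOR and yet be a disease-control success. SAP VIII.A.3 places the DCR lines in the ORR table, so both results would appear together.

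**5. Size per affected patient.** The documents give no count, so one or two patients are assumed. The change in DCR is k/n:

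| n | Source of n | k = 1 | k = 2 |
|---|---|---|---|
| 6 | Module 3 arm (SAP IV.C) | 16.7 points | 33.3 points |
| 18 | Module 2, approximate (SAP IV.C) | 5.6 points | 11.1 points |
| 30 | Module 1 maximum (SAP IV.C) | 3.3 points | 6.7 points |

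SAP VIII.B uses two-sided 95% Clopper-Pearson limits: lower = Beta(0.025; x, n − x + 1), upper = Beta(0.975; x + 1, n − x). For a hypothetical six-patient arm, 2/6 = 33.3% (4.3 to 77.7) becomes 1/6 = 16.7% (0.4 to 64.1) once one patient is reclassified.

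**The case against.** **The exposed group is narrow.** This stands. Patients who switch because of documented progression are already excluded by the carry-forward rule. A reader might infer that any SD at the second scan counts whatever came before, and the SAP does not support that. Entry also requires that conventional treatment is no longer considered appropriate (protocol 2.1.1), which makes a switch before progression within 12 to 16 weeks less likely. It does not rule one out, since protocol 2.3.1.3 mentions later investigational drugs.

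**DCR is not the primary endpoint.** This also stands. Protocol 1.2.1 calls it primary for the monotherapy arm, and a reader might rest the importance of this point on that. The operative objectives (protocol 1.9.1 and 1.9.2, SAP II) make safety and tolerability primary and anti-tumour activity secondary and preliminary. No hypothesis is tested.

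**The Module 1 figure of 5/18 is not an affected DCR.** Agreed. Protocol 1.7.1.1 reports SD at any time among RECIST-evaluable patients, not week-12 disease control among all dosed. A relative overstatement derived from it has no basis.

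**ORR is largely protected.** Agreed. A reader might treat it as equally exposed, but the first CR or PR must arise within the BOR window. Only a confirmation scan taken after a new therapy began could be affected.

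**Ignoring new therapy is a coherent choice, as PFS shows.** It is coherent where it is declared. PFS declares it; DCR does not, and BOR in the same table takes the narrower course. The precedent therefore does not settle DCR.

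**Cases would be visible in listings and swim-lane plots.** True, but a reader would have to correct the reported rate by hand.

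**Conclusion.** The point holds as a cheap improvement. As written, the DCR rule credits RXC004 with SD or better seen after another anti-cancer therapy has begun, provided there was no earlier PD. No other text prevents it. This follows from silence; the SAP does not expressly instruct that such scans be counted.

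Each affected patient adds 16.7 points in a 6-patient arm and about 5.6 points among 18. These are illustrations that assume one case. The true number is unknown, and if it is zero nothing changes. The intervals at these sample sizes are wide and overlap heavily, so the matter is one of attribution and clarity in a descriptive secondary endpoint. It does not threaten the trial's primary conclusions.

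**What to change.** Add to SAP VIII.A.3 and protocol 9.2.1:

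> Only RECIST assessments dated before the start of any subsequent anti-cancer therapy count toward disease control, including a later scan used in place of a missing or NE second scan. A patient who starts such therapy before the relevant scan remains in the denominator and is counted as not having disease control at that time point.

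As a minor addition to SAP VIII.A.1, apply the same date limit to post-treatment scans used only to confirm a CR or PR first seen on study treatment. Leave PFS unchanged.

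Apply the rule to modules not yet locked. SAP I indicates that Module 1 was locked before the Module 2 and 3 changes, so for Module 1 report the restricted DCR as a documented sensitivity line.

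The cost is a short SAP insertion and one date comparison, assuming that the start date is among the subsequent-therapy details already collected. DCR or ORR may be slightly less favourable. DCR and PFS will also treat new therapy differently: a patient could be progression-free at week 12 and still count as not controlled. The SAP should say so.
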